5.0 TREATMENT OPTIONS

Candidates for TMVR with LAMPOON have no good alternative treatment options. They are not eligible for definitive treatment using surgical mitral valve repair or replacement. They are not eligible for TMVR using off-label THV devices because of the risk of LVOT obstruction. They are not deemed suitable for an alternative investigational preemptive treatment through transcoronary alcohol septal ablation/infarction/debulking because of anatomic limitations and/or the attendant hazard and myocardial injury and requisite 4-6 weeks delay in highly symptomatic patients.

6.0 STUDY DESIGN

6.1 Schematic of Study Design

6.2 Overview of Study Design

This is a prospective, open-label, single-arm, multi-center, investigator-initiated, independently-adjudicated trial of LAMPOON immediately before transcatheter antegrade transseptal TMVR in subjects otherwise ineligible for TMVR.

Candidates will be identified by the participating structural heart disease programs. In evaluation of mitral valve disease, candidates will undergo clinical evaluation including transesophageal imaging and contrast-enhanced gated cardiac CT. Eligibility will be reviewed and proposed by the local multidisciplinary heart teams. Candidates will then undergo central eligibility review by the sponsor and designated investigators. If deemed eligible, candidates will be offered participation in the study.

Once enrolled, subjects will undergo baseline assessment, which includes quality of life questionnaires, walking tests, frailty assessments, and blood tests.

Subjects will be admitted to the hospital and undergo TMVR with LAMPOON. They will undergo endpoint assessment before discharge, after 30 days, 6 months, and then 12 months.

6.3 LAMPOON TMVR Procedure

The TMVR procedure is planned from a contrast-enhanced CT of the heart to select a suitable transcatheter heart valve size, predict suitability of the mitral annular landing zone, and predict post-TMVR LVOT obstruction related to TMVR encroachment and long or redundant anterior mitral valve leaflets. The LAMPOON procedure uses the same clinical CT exam to choose a crossing point for the anterior mitral valve leaflet and to select appropriate fluoroscopic projection angles and radiographic landmarks.

The procedure is performed under general anesthesia or under moderate sedation at the discretion of the institutional heart team. The LAMPOON procedure has three steps: (1) leaflet traversal with a guidewire, followed by (2) leaflet laceration, immediately followed by (3) TMVR. These are all guided by fluoroscopy combined with TEE or intracardiac echocardiography.

First catheter access is obtained typically via three transfemoral arterial (two for LAMPOON and one for LV hemodynamics and angiography) and two transfemoral venous introducers sheaths (one for TMVR and another for temporary transvenous pacing). After anticoagulation with heparin or equivalent to achieve an activated clotting time > 300s, transvenous atrial transseptal puncture is performed under echocardiographic guidance. Atrial septostomy is performed, and a percutaneous transapical rail is established at operator discretion as needed.

Hemodynamic and echocardiography measurements are recorded at baseline including gradients across the mitral and aortic valves and LVOT, and severity of valvular regurgitation.

Two retrograde catheters are positioned, using a guidewire rail with the antegrade transseptal catheter as needed, in the LVOT and LA respectively. Catheter and echocardiographic maneuvers are performed at operator discretion to assure traversal of the major orifice of the mitral valve. Typically, these maneuvers include advancement of a large-volume inflated balloon tip catheter from the LA to the LVOT under angiographic and echocardiographic guidance to assure no entrapment. Next a snare catheter is positioned in the mitral inflow via the LA catheter. An insulated transcatheter electrosurgery catheter system (typically a rigid 0.014" guidewire inside a polymer jacket wire convertor) is positioned against the anterior mitral leaflet target at the A2 scallop, using fluoroscopic and echocardiographic guidance. Nonionic conductive flush (dextrose 5%) can be administered as needed via the guiding catheters to reduce guidewire char and thromboembolism.

Traversal is accomplished by transcatheter electrosurgery by connecting the back end of the 0.014" guidewire to an electrosurgery pencil during short bursts of "pure, cutting" radiofrequency energy at approximately 50W. The guidewire is repositioned as needed until it crosses the mitral leaflet and is snare-retrieved.

Next the polymer jacket wire convertor is withdrawn, and the traversal wire is modified at the bedside by the operator by (1) denuding a non-circumferential segment ~2mm in length, 90° arc and (2) kinking the denuded segment to enforce its position at the inner curvature of the intended guidewire lacerating surface. Next the polymer jacket radiopaque marker tip is locked adjacent to the kinked denuded shaft segment. Next the ensnared guidewire is externalized to position the lacerating surface across the base of the leaflet.

Next, at operator discretion, the transcatheter heart valve may be positioned in the left atrium or across the mitral valve before or after the laceration step. If before, the operator assures no entrapment of the TMVR system with the laceration system of catheters.

Laceration is performed by positioning the laceration surface along the intended leaflet base and applying tension on both free ends of the guidewire, while simultaneously apply electrosurgery energy in short bursts, until the laceration is complete and the guidewire is free.

Hemodynamics are recorded quickly after laceration before TMVR. Then TMVR is performed using established techniques¹⁴ typically during rapid ventricular pacing. The THV device is used outside the manufacturer instructions for use, in that it is implanted in the mitral position. The device size and inflation volumes are selected and applied at the discretion of the operator. A balloon flaring maneuver is encouraged to reduce the likelihood of THV embolization into the left atrium.

Completion hemodynamics and echocardiography are recorded. Adjunctive transcatheter procedures, including to close paravalvular leaks and to close iatrogenic atrial septal defects, are performed at operator discretion and details are recorded. Finally, percutaneous femoral artery and vein vascular hemostasis is obtained and the subject convalesces in the appropriate inpatient recovery unit.

Before discharge, follow-up transthoracic echocardiography is recorded. A single contrast-enhanced CT of the heart is obtained before discharge if renal function allows, otherwise it is deferred as long as 30-days. Blood tests are recorded for research only as obtained for medical care.

After discharge, subjects are recommended to undergo at least 3 months of warfarin anticoagulation with a target INR of 2-3, along with aspirin 81mg indefinitely. These recommendations are superseded by indications for long-term anticoagulation (such as atrial fibrillation), or P2Y12 inhibitors.

6.4 Time and Events Schedule

	Screening	Baseline	Day 0	Inpatient	30 d (±14d) FU	6 mo (± 30 Days)	12 mo (± 4 wk)	2 yrs (± 1 mo) (range)	3 yrs (± 1 mo)	4 yrs (± 1 mo)	5 yrs (± 1 mo)
Baseline informed consent:		Х									
Multidisciplinary heart team eligibility determination		х									
Baseline clinical assessment		Х									
6 minute walk test		Х			Х		Χ				
Kansas City Cardiomyopathy Questionnaire (KCCQ)		х			Х		Х				
NYHA Classification		Х			Х	Х	Χ				
Frailty tests: Katz ADL, 5MW, Albumin		Х									
Blood tests: CBC, Platelet, Haptoglobin, Liver panel, Chemistry Panel, Albumin, LDH, BNP/Pro-BNP (as clarified below)		Х		Х	Х	Х	Х				
Vital signs and in-person visit		Х			Χ	Χ	Χ				
Cardiac CT contrast-enhanced gated dy- namic	Screening or baseline	Screening or baseline		Inpatient or 30D	Inpatient or 30D						
Transesophageal echocardiogram	Screening or baseline	Screening or baseline	Х								
TMVR with LAMPOON			Χ								
Surface echocardiogram	Screening or baseline	Screening or baseline		Х	Х	Х	Х				
ECG		Х		Х	Χ	Х	Χ				
Adverse event assessment				Х	Χ	Χ	Χ				
Vital status and clinical echo or report								Χ	Χ	Χ	Χ

Subjects would receive continuing care from their primary physicians with consultant input as requested from the structural heart disease program.

For subjects who die, necropsy evaluation is requested to examine the heart at NIH.

6.4.1 Applicability to CMS Coverage Evaluation Determination

Requirements for a Coverage Evaluation Determination (CED) by Centers for Medicare and Medicaid Services (CMS) are reviewed here. (1) The principal purpose of the study is to test whether LAMPOON TMVR meaningfully improves health outcomes of affected beneficiaries. (2) Scientific evidence supports the study rationale. (3) The study does not unjustifiably duplicate existing knowledge. (4) The study design is methodologically appropriate and sufficiently powered to answer the research question. Even though the sample size is not statistically driven, the experience is expected to set the standard for TMVR using commercially available valves. (5) The study sponsor is capable of completing the study. (6) The study complies with applicable Federal Law and obtains meaningful informed consent regarding risks and the data disposition. (7) The study is conducted ethically. (8) There is a written study protocol that adheres to CMS standards. (9) The study does not test exclusively toxicity nor natural history, although the studied condition is lethal. (10) The study will be registered in clinicaltrials.gov. (11) The study indicates results will be released within 12 months of completing enrollment, irrespective of outcome. (12) The study protocol explicitly discusses beneficiary subpopulations affected by TMVR LAMPOON, especially medically underrepresented groups, with a recruitment and retention plan.

6.5 Visit Schedule

All activities except TMVR/LAMPOON, Consent, KCCQ, and Adverse event assessment are performed for standard clinical care.

Timing	Event						
Screening (any time)	Medical, Surgical and Interventional Assessment, determination and documentation that the subject has no other options for MVR						
Screening (any time)	Cardiac CT contrast enhanced, gated dynamic						
Screening (any time)	Transesophageal echocardiogram						
Screening (any time)	Multidisciplinary heart team eligibility determination and documentation						
Baseline (within 30 days of procedure)	Research Informed Consent to include documented Inclusion and Exclusion criteria						
Baseline (within 30 days of procedure)	 Clinical Assessment to include: Vital signs Baseline symptoms Medication Assessment NYHA Classification Other co-morbidities that could preclude the subject living the required 6 months post procedure ECG Surface echocardiogram-transthoracic 						

Baseline (within 30 days of procedure)	Clinical Blood tests: CBC Platelets Haptoglobin Liver Function panel Chemistry panel Troponin Albumin LDH BNP/Pro-BNP Pregnancy test if applicable					
Baseline (within 30 days of procedure)	6-minute walk					
Baseline (within 30 days of procedure)	Kansas City Cardiomyopathy Questionnaire (KCCQ)					
Baseline (within 30 days of procedure)	Frailty Tests: Katz ADL, 5-meter walk, Albumin					
Day 0	TMVR with Lampoon procedure					
Within 48 hours of Lampoon TMVR	Blood work to include: • Troponin					
Pre-discharge	 Clinical Evaluation to include: Cardiac CT scan contrast enhance, gated dynamic- if not clinically suitable then re-schedule for 30 Day follow up visit Surface echocardiogram ECG Medication Assessment Adverse Event Assessment 					

30-day (±14 days)	Clinic/office visit to update subject's vital status to include:
	Vital signs
	• ECG
	Medication Assessment
	NYHA Classification
	Surface Echocardiogram
	Cardiac CT scan contrast enhance, gated dynamic- if not conducted
	pre-discharge for clinical reasons
	6-minute walk
	Kansas City Cardiomyopathy Questionnaire
	Blood work to include:
	CBC with platelets
	Haptoglobin
	Chemistry Panel
	PT INR
	BNP/Pro-BNP
	Adverse Event Assessment
6-month (±30 days)	Clinic/office visit to update subject's vital status to include:
	Vital signs
	NYHA Classification
	• ECG
	Medication Assessment
	Surface Echocardiogram
	Blood work to include:
	CBC with platelets
	Haptoglobin
	PT INR
	BNP/Pro-BNP
	Chemistry Panel
	Adverse Event Assessment

12 month (±30 days)	Clinic/office visit to update subject's vital status to include:
	 Vital signs ECG Medication Assessment NYHA Classification Surface Echocardiogram 6-minute walk
	 Kansas City Cardiomyopathy Questionnaire Blood work to include: CBC with platelets Haptoglobin Chemistry Panel PT INR BNP/Pro-BNP Adverse Event Assessment
Annually years 2-5 (\pm 30 days)	 Telephone call or local physician contact to assess vital status Collect results or images of clinical echocardiogram

7.0 ELIGIBILITY ASSESSMENT

7.1 Inclusion Criteria

- Adults age ≥ 21 years
- Severe symptomatic native mitral valve failure after mitral annuloplasty repair or related to mitral annular calcification.
- Unacceptably high or prohibitive risk for surgical mitral valve replacement and indicated for transcatheter mitral valve replacement (TMVR) as determined by the multidisciplinary institutional heart team, including at least one cardiovascular surgeon who has examined the patient
- High or prohibitive risk of LVOT obstruction (predicted neo-LVOT less than 200 mm²⁾ or transcatheter heart valve dysfunction from long/redundant anterior mitral valve leaflet, as determined by the multidisciplinary institutional heart team.
- Anatomic eligibility for LAMPOON based on core lab assessment of the baseline CT and echocardiogram.
- Concordance of the study selection team

7.2 Exclusion criteria

- Subjects unable to consent to participate, unless the subject has a legally authorized representative
- Subjects unwilling to participate or unwilling to return for study follow-up activities.
- Predicted neo-LVOT created by the Sapien 3 skirt, after LAMPOON, less than 150 mm²

- TAVR within 6 weeks
- Intended concurrent structural heart procedure, such as aortic or tricuspid valve implantation
- Pregnancy or intent to become pregnant prior to completion of all protocol follow-up procedures

7.3 Rationale for selection criteria

The selection criteria allow enrollment of the intended population with little anticipated selection bias. Instead of functional or geometric selection criteria, the study will enroll all subjects deemed otherwise suitable for TMVR yet at risk of the problem to be addressed by LAMPOON, the investigational procedure. Planned concurrent valve procedures such as TAVR are disallowed based on a recent fatal adverse event described in section 4.0.

In Amendment C, an additional exclusion criterion was added. This considers whether the fabric-covered "skirt" of the Sapien 3 transcatheter heart valve might obstruct the left ventricular outflow tract despite successful LAMPOON. Candidates who might continue to have an obstructive "skirt neo-LVOT" are excluded. This amendment also formalizes a threshold neo-LVOT for selection.

The inclusive selection criteria and geographic extent of enrolling sites are expected to allow recruitment of a diverse economic, ethnic, and racial mix of patients that reflects the incident disease. Specifically, the results are expected to be generalizable to Medicare and Medicaid beneficiaries because of age and disease-related disability.

8.0 Strategies for Recruitment

Subjects will be recruited from the Structural Heart Disease clinical programs of the participating hospitals.

The distribution of planned enrolling sites assures accessibility of the trial to ethnically, racially, and economically diverse populations. The study will track sex, age, ethnicity, and racial background of subjects.

Once recruited, subject retention rate is expected to be high because follow-up activities are not onerous and are timed to correspond with routine follow-up medical care, without prohibitively expensive follow-up testing.

One site investigator, [name], is the Principal Investigator of the MITRAL study (NCT02370511) of TMVR which specifically excludes subjects suitable for this study. She estimates as many as half of her study candidates fail screening because of predicted LVOT obstruction [[name], Personal Communication, October [2016]. [name] will recommend referring physicians refer to sites participating in this study.

During the early clinical development of the LAMPOON procedure, 9 clinical patients were treated in approximately 5 months at two centers, which suggest the recruitment objectives will be met.

9.0 SAMPLE COLLECTION, STORAGE AND TRACKING PLAN

Imaging data (from angiography, CT, and echocardiography) constitute the only specimens to be collected. CT examinations performed for clinical evaluation prior to signing informed consent may be used as the baseline scan.

CT and Echocardiography data will be analyzed at the Henry Ford Hospital Core Laboratory as well as to the NHLBI for concurrent analysis. These data will be transmitted on electronic media such as a DVD via carrier or using secure file transfer mechanisms abiding HIPAA and local institutional standards (such as SFTP or https://secureemail.nih.gov).

Imaging data are stored according to local institutional standards.

Copies of imaging studies are transmitted to a central facility (NHLBI) using secure HIPAA compliant methods and are stored in a secure Picture Archive Computer System (PACS), known as NHLBIPACS.

Necropsy specimens will be handled according to local institutional medical standards and will be disposed accordingly.

9.1 Data transfer to collaborators

De-identified and de-linked data and images will be posted at the NHLBI Cardiovascular Intervention Structural Heart Image Data Repository ([name] or equivalent). They are provided for the purpose of medical education and research. They are de-identified and de-linked, so that patients can not readily be identified, and are therefore not considered human research subjects research data under US 45CFR§46.102(f).

De-identified and de-linked images will also be transferred to collaborating investigators at academic and industry sites. They are provided for the purpose of medical education and research. They are de-identified and de-linked, so that patients can not readily be identified, and are therefore not considered human research subjects research data under US 45CFR§46.102(f).

These recipients include all enrolling site investigators and:

[name]	Georgia Institute of Technology	Atlanta, Georgia, USA
[name]	3mensio Pie Medical Esaote	Bilthoven, Netherlands
[name]	Transmural Systems	Andover, MA, USA
[name]	Cook Medical	West Lafayette, IN, USA
[name]	UCSD Rady Childrens Hospital	San Diego, CA

9.2 Core Laboratories

Core laboratories are employed for centralized and systematic analysis of key imaging data, including echocardiography and CT.

Amendment E adds a core laboratory #2 for analysis of CT. Measurements from core laboratory #1 are superseded by core lab #2.

10.0 BIOSTATISTICAL AND ANALYTICAL CONSIDERATIONS

10.1 Sample Size

The sample size is not statistically derived. This is a safety and feasibility study that enables patient access to off-label use of a medical device, when these patients have no other good medical options to treat

symptomatic mitral valve failure. An arbitrary initial sample size of 30 is proposed, and will be increased if needed, until a commercial solution is found for medical care.

Up to 60 subjects will be consented until 30 subjects undergo attempted LAMPOON TMVR in this protocol.

We will adhere to the extent possible to consensus guidelines that have been established for the analysis and reporting of transcatheter mitral valve repair investigational procedures. 19, 20

10.2 Study Analysis

Clinical events are classified by the local site Principal Investigator and confirmed by the Principal Investigator. The results of the study will be released within 12 months of study completion.

Analyses will be stratified according to the setting for TMVR, whether valve-in-ring, valve-in-band, or valve-in-MAC.

The study will be analyzed using descriptive statistics, including a case-by-case narrative summary of major adverse events. Afterwards, we will survey for parameters associated with an increased risk of major adverse events.

Primary and secondary endpoints will also be analyzed separately among patients with- and without- mitral annular calcification as the primary indication for TMVR.

10.2.1 Primary endpoint

The primary endpoint is Technical success ACCEPTABLE (measured at exit from the catheterization laboratory)¹⁹. All of the following must be present:

- Successful LAMPOON traversal and laceration; and
- Peak LVOT gradient < 50 mm Hg; and
- Absence of procedural mortality; and
- Successful access, delivery, and retrieval of the LAMPOON device system; and
- Successful deployment and correct positioning of the first intended device; and
- Freedom from emergency surgery or reintervention related to the device or access procedure.

The first two factors are modifications of the MVARC (mitral valve academic research consortium) consensus endpoint¹⁹, specific for LAMPOON procedure.

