1.0 Protocol Summary

Title:	NHLBI LAMPOON Study: Intentional laceration of the anterior mitral leaflet to prevent left ventricular outflow tract obstruction during transcatheter mitral valve implantation
Précis:	Transcatheter mitral valve replacement (TMVR) can cause life-threatening complications such as left ventricular outflow tract obstruction and transcatheter heart valve dysfunction, in cases of extreme septal displacement of the anterior mitral valve leaflet (AML).
	LAMPOON is a new catheter technique to split the AML and prevent iatrogenic left ventricular outflow tract obstruction immediately before TMVR. It mimics surgical chord-sparing AML resection. It has been used successfully in a small number of patients
Hypothesis:	LAMPOON enables transcatheter mitral valve implantation (TMVR) without life-threatening left ventricular outflow obstruction or transcatheter heart valve dysfunction
Objectives:	Technical success (defined below) of LAMPOON-TMVR Safety (Freedom from MACE to hospital discharge and 30days) of LAM- POON-TMVR
Safety Endpoints	Survival to discharge Survival to 30days Freedom from MACE (according to MVARC)
Feasibility Endpoints	Procedure technical success (TMVR with successful LAMPOON, without requiring bailout cardiac surgery or bailout septal reduction)
	Stratified analysis based on predicted LVOT obstruction or predicted THV dysfunction ("hanging leaflet")
Population:	Patients with native mitral valve failure (regurgitation or stenosis) after surgical mitral annuloplasty or from native mitral annular calcification, requiring transcatheter mitral valve replacement because of prohibitive risk of mitral valve surgery

Inclusion Criteria	Undergoing TMVR for valve-in-ring, valve-in-band, or valve-in MAC:
	Adults age ≥ 21 years
	Severe symptomatic native mitral valve failure after mitral annuloplasty repair or related to mitral annular calcification.
	Transcatheter mitral valve replacement (TMVR) is felt indicated by the multi- disciplinary institutional heart team, including at least one cardiovascular surgeon who has examined the patient
	High or prohibitive risk of LVOT obstruction (predicted neo-LVOT less than 200 mm ²⁾) or transcatheter heart valve dysfunction from long/redundant anterior mitral valve leaflet, as determined by the multidisciplinary institutional heart team.
	Anatomic eligibility for LAMPOON based on core lab assessment of the base-line CT and echocardiogram.
	Concordance of the study selection team

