10.2.2 Co-Primary endpoint

Based on feedback from the FDA, the co-primary endpoint is Technical Success OPTIMAL (measured at exit from the catheterization laboratory). This differs from "Technical Success ACCEPTABLE" only in the magnitude of the peak LVOT gradient.

All of the following must be present:

- Successful LAMPOON traversal and laceration; and
- Peak LVOT gradient < 30 mm Hg; and
- Absence of procedural mortality; and
- Successful access, delivery, and retrieval of the LAMPOON device system; and

- Successful deployment and correct positioning of the first intended device; and
- Freedom from emergency surgery or reintervention related to the device or access procedure.

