11.0 ADVERSE EVENT REPORTING

11.1 Definitions

Adverse events: Any untoward medical occurrence in a human subject, including any abnormal sign (e.g., abnormal physical exam or laboratory finding), symptom, or disease, temporally associated with the subject's participation in the research, whether or not considered related to the subject's participation in the research.

This will include:

- Expected events related to the subject's disease process during active enrollment in the research protocol and do not directly result from use of the investigational device or study.
- Procedural events directly related to the cardiac catheterization procedure and recovery from the procedure and do not directly result from use of the investigational device.

Serious Adverse Event (SAE): A serious adverse event that results in any of the following and NOT directly related to the device. This includes any event that

- Results in death
- Is life-threatening (places the subject at immediate risk of death from the event as it occurs);
- results in in-patient hospitalization or prolongation of existing hospitalization;
- results in a persistent or significant incapacity;
- results in a congenital anomaly/birth defect (not relevant to this study); or
- based upon appropriate medical judgment, may jeopardize the subject's health and may require medical or surgical intervention to prevent one of the other outcomes listed in this definition.

Adverse Device Effect (ADE): Any untoward or unintended response to a medical device. This definition includes any event resulting from insufficiencies or inadequacies in the instructions for use or the deployment of the device or any event that is a result of user error.

During this clinical investigation an event should be considered related to the device when it is the result of:

- LAMPOON procedure
- Edwards Sapien 3 transcatheter heart valve or accessories
- Asahi-Intecc Astato XS 20 guidewire

An event will be considered NOT related to the LAMPOON procedure when it is the result of:

- A pre-existing medical condition
- Clearly attributable to TMVR but not LAMPOON part of procedure (example: commissural paravalvular leak)

Anticipated Adverse Device Effects (AADEs): An AADE is an adverse event with a reasonable possibility that the device or procedure caused or contributed to the event. The following AADEs are considered anticipated based on previous human experience:

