- LAMPOON device failure including failure to traverse, to lacerate, or to position catheters or guidewires
- Valve malposition, reposition, dislocation, migration, or embolization or deployment in unintended location
- Interatrial shunt

- LVOT gradient
- Aortic valve injury
- Paravalvular leak
- Atrial-ventricular conduction defects to include bundle branch block and complete heart block requiring placement of a temporary or permanent pacemaker
- Cardiac arrhythmia including ventricular tachycardia and atrial fibrillation
- Transient myocardial dysfunction attributed to rapid ventricular pacing required for mitral valve implantation, including brady-asystole or pulseless electrical activity, or requiring cardiopulmonary resuscitation
- Angina and myocardial ischemia
- Coronary artery obstruction or injury that may require intervention
- Myocardial infarction
- Congestive heart failure or BNP elevation
- Cardiogenic shock that may require intervention
- Infective endocarditis
- Left ventricular or left atrial perforation
- Pericardial effusion or tamponade
- Hypertension
- Hypotension requiring vasopressor support or mechanical circulatory support
- Stroke or TIA or seizure
- Hemolysis which requires transfusions and which requires confirmatory dramatic schizocytes and haptoglobin decline
- Low platelets or thrombocytopenia or increased or reduced leukocytes
- Mechanical injury to the myocardium, access vasculature, cardiac valves that may require intervention or that may elevate Troponin
- Bleeding causing anemia and blood transfusions
- Mitral valve thrombosis
- Embolization of air, calcific valve material, atheroma, or thrombus to coronaries, brain, limbs, or viscera causing myocardial infarction, stroke, or limb ischemia
- Retroperitoneal bleed or hematoma or access site injury
- Contrast-induced nephropathy requiring temporary or permanent hemodialysis or medical treatment
- Volume overload, pleural effusion, or dyspnea from procedure-related volume perturbations
- Respiratory failure requiring oxygen or mechanical support or mechanical ventilation
- Infection including access site or urinary or pulmonary or including sepsis
- Pain including back pain and access site and generalized
- Cardiac arrest
- Death

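### Must the plan say whether leak or septal-defect closures done in the catheterization laboratory count against technical success?

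*Combined protocol and SAP*

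**What the plan says.** Section 10.2.1 defines the primary endpoint by six conditions that must all hold, "measured at exit from the catheterization laboratory". The last is "Freedom from emergency surgery or reintervention related to the device or access procedure". The section says that only the first two conditions (laceration success and the gradient limit) were adapted for this study. The other four are therefore presented as MVARC consensus wording. Section 10.2.2 repeats the list for the co-primary endpoint, which differs "only in the magnitude of the peak LVOT gradient".

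Section 6.3 describes the index procedure. After valve implantation and before vascular hemostasis it says: "Adjunctive transcatheter procedures, including to close paravalvular leaks and to close iatrogenic atrial septal defects, are performed at operator discretion and details are recorded".

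Section 1.0 gives a one-line version among the feasibility endpoints: "Procedure technical success (TMVR with successful LAMPOON, without requiring bailout cardiac surgery or bailout septal reduction".

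Section 11.1, on adverse events, counts an event as device-related when it results from, among other things, the "Edwards Sapien 3 transcatheter heart valve or accessories". It counts an event as not related to the LAMPOON procedure when it is "Clearly attributable to TMVR but not LAMPOON part of procedure (example: commissural paravalvular leak". Its list of anticipated device effects includes paravalvular leak and "Interatrial shunt".

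Section 10.2.3 lists paravalvular leak within an exploratory endpoint. Section 10.2.5 has an independent committee review primary endpoints.

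**The concern.** The closures in Section 6.3 happen before laboratory exit, so they fall inside the window in which both endpoints are judged. If a leak is device-related because the valve is on the device list, and a septal defect is access-related because it comes from the transseptal route, closing either one looks like a reintervention that fails the subject. Section 1.0 names only bailout surgery and septal reduction, so it would seem to count the same subject as a success.

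The literal rule would also behave oddly. No condition contains a leak grade, so a leak closed in the laboratory would fail. The same leak left open would pass, provided the valve is judged correctly positioned. The headline rate of an open-label study would then depend partly on the operator's choice. Section 10.3 describes severe leak as much less of a risk in ring and band cases than in MAC cases, and Section 10.2 calls for separate results with and without MAC. The reading adopted could therefore create or remove a difference between those groups. The co-primary endpoint offers no protection, because it shares the condition.

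**Working it through.** **1. Is failure the only reading?** The plan defines neither reintervention nor the device in this condition. Four readings are tenable:

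| Reading of the last condition | In-lab leak or septal-defect closure | In-lab septal reduction as bailout |
|---|---|---|
| Any same-session procedure tied to the valve or the access route, using the Section 11.1 device list | Fails | Fails |
| Emergency qualifies reintervention as well as surgery | Passes unless an emergency | Fails |
| Closures belong to the index procedure, where Section 6.3 places them | Passes | Can still fail; Section 6.3 does not name it |
| Reintervention means a later return | Passes | Passes, against Section 1.0 |

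The fourth reading is weak, because little could be captured by laboratory exit and it conflicts with Section 1.0. The first three survive, so failure is one reading and not an established consequence.

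**2. How far does Section 11.1 reach?** It governs adverse-event attribution. Its anticipated-effects list also contains hypertension, pain and low platelets, so appearing there says little about endpoint failure. Section 10.2.5 asks the committee to classify relatedness to LAMPOON, and Section 11.1 treats a leak clearly due to TMVR as not LAMPOON-related. That pulls towards passing, but it is not decisive while the valve stays on the device list. In the endpoint list itself, the word device is used once for the laceration system and once for the implant.

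**3. Does Section 1.0 contradict Section 10.2.1?** The Section 1.0 line also omits the gradient limit, procedural death and placement of the first device. Taken as a complete definition, it would pass a subject with a gradient of, say, 80 mm Hg, whom Section 10.2.1 fails at its limit of 50. It is an abbreviated summary that is silent on closures.

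**4. Size.** The plan states no success rate or power figure to reproduce. The denominator is 30 attempted procedures (Section 10.1).

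- Shift per reclassified subject: 1/30 = 3.3 points, on both endpoints.
- Chance that at least one of 30 subjects is affected, 1 − (1 − p)^30, and expected number, 30p, at assumed closure rates p:

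| p (assumed) | At least one | Expected number |
|---|---|---|
| 2% | 45.5% | 0.6 |
| 5% | 78.5% | 1.5 |
| 10% | 95.8% | 3 |
| 20% | 99.9% | 6 |

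- If 27/30 succeed when closures are not counted (assumed), with exact 95% intervals:

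| Closures among the successes | Rate | 95% interval |
|---|---|---|
| 0 | 27/30 = 90.0% | 73.5–97.9 |
| 1 | 26/30 = 86.7% | 69.3–96.2 |
| 3 | 24/30 = 80.0% | 61.4–92.3 |
| 6 | 21/30 = 70.0% | 50.6–85.3 |

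- Strata, assuming a 15/15 split, all else met and no closures in ring/band: 15/15 = 100% (78.2–100) against 14/15 = 93.3% (68.1–99.8) with one MAC closure, or 11/15 = 73.3% (44.9–92.2) with four. The gap runs from 6.7 to 26.7 points, and the intervals overlap even at the extreme.

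The only hint of frequency is in Appendix A: the leak row has score 6 and severity 2, so likelihood 6/2 = 3, labelled common. That describes leaks, not closures.

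**5. What depends on the number?** Section 10.2 specifies descriptive statistics with case narratives of major adverse events. The stopping rules in Sections 10.3.1 and 10.3.2 use 30-day mortality only. No performance goal is set for technical success.

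**The case for a change.** The best case for a change rests on timing. Assessment ends at laboratory exit, so the condition can catch only same-session procedures, which makes the literal reading a natural one. Review by the committee does not fully settle the matter: its stated task is relatedness to LAMPOON, whereas the condition asks about the device or the access route. The protocol gives it no rule for closures, and Section 10.2 leaves first classification to the site investigator. With 30 subjects, three reclassifications move the rate by ten points, and the effect could fall mainly on MAC cases.

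Part of this stands. The gap is real, the literal reading is fair, and under that reading a closed leak is penalized while an open one is not. Three things do not stand. The claim that these subjects fail is not established by the text. The conflict with Section 1.0 rests on treating a summary line as a full definition. The unequal handling of closed and open leaks is a feature of a composite presented as consensus wording, kept for comparison with other trials (Section 10.2.4), and is not a demonstrated error. The consensus source may define the term, but it is not available here. Ruling closures in lowers the rate because of events from the valve implant, while ruling them out could weaken comparability, so a forced choice would be a trade-off and not a correction.

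**Conclusion.** No change is needed. The plan leaves undefined how in-lab closures count, and analysts can fill that gap sensibly. The committee reviews each primary endpoint, closures and completion echocardiography are recorded for every case, and leak is reported separately, so untreated leaks are not hidden. Anyone reporting the study can say how closures were counted and give the rate both ways without new data. If that choice is made after outcomes are known, it should be described as such.

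The firm figure is 3.3 points per reclassified subject. Closure rates, the 27/30 baseline, the 15/15 split and the number of MAC closures are all assumptions. The conclusion rests on the endpoint staying descriptive, with no decision rule attached. It concerns endpoint counting only and says nothing about when a closure should be done.
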